**F. Variables to Create / Calculate**

Description
BMI
Area –under- curve (from pain scores in PACU)
Analgesic equivalents of prescribed opioids
Total length of all plates implanted
Total number of screw holes of all plates implanted
Duration of surgery
Duration of PACU stay

**G. Data Sources**

- EPIC chart review
- SEFAS scores exported from REDCap
- Opioid equivalency values: <http://www.globalrph.com/narcotic.htm>

**H. Software Used (with References) and Specialized Macros (with References)**

Calculation of basic statistical parameters, t-tests, Mann-Whitney tests, and Fischer's exact test will be conducted using GraphPad Prism (GraphPad Software, Inc.) or SAS 9.4 (SAS Institute).

## I. Mock tables to be produced

Table 1: Descriptive table of demographics of experimental and control groups prior to intervention.

Description	Control (N = ***) 	Experimental (N = ***) 	p value
Age at ankle surgery (years)			
Weight at time of surgery			
Height at time of surgery			
BMI at time of surgery			
Race			
Ethnicity			
Ankle fracture: number of malleoli affected			
Grade of injury (defined as closed injury, or open injury with Gustilo Anderson classification grade 1, grade 2, grade 3a, grade 3b, grade 3cr) 			
Time in surgery			
Estimated blood lost in surgery			
Number of plates implanted			
Total length of plates implanted			
Total number of screw holes in implanted hardware			

Mean, SD, median, interquartile range for continuous variables, number and % per group for categorical variables.

 Converted to ordinal scale 1 – 6

Table 2 Pain outcomes

Description	Control (N = ***)	Experimental (N = ***)	p value
Opioid medication use in PACU: analgesic equivalents			
Time in PACU			
PACU discharge status (home, rehab facility, hospital) 			
PACU Pain score AUC			

Average Pain score in PACU			
SEFAS score (2 week)			
Pain medication use analgesic equivalents (2 week)			
SEFAS score (3 month)			
Pain medication use analgesic equivalents (3 month)			
SEFAS score (6 month)			
Pain medication use analgesic equivalents (6 month)			
SEFAS score (12 month)			
Pain medication use analgesic equivalents (12 month)			
Number (%) with any chronic pain diagnosis at 12 months			

 Converted to ordinal scale 1 – 3

Table 3 Other outcomes

Description	Control (N = ***)	Experimental (N = ***)	p value
Number (%) requiring re-operation			
Number (%) : Indication for re-operation (infection, non-union, hardware failure, hardware removal, other)			
Wound healing status at first FU (dehiscence, cellulitis , deep infection, healing well, other) 			
Wound healing status at second FU (dehiscence, cellulitis , deep infection, healing well, other) 			
Weight bearing current status at first FU [full, assisted (cane, walker, boot), non (crutch)] 			
Weight bearing current status at second FU [full, assisted			

(cane, walker, boot), non (crutch)] 			
---	--	--	--

 Converted to ordinal scale

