Randomization: We will use a block-stratified randomization schedule with blocks of sizes 2 and 4. The West Chester and Uptown locations will have separate randomization schedules as it is thought the two locations provide somewhat different populations, making it desirable to have approximately equal numbers in the control and experimental groups at each site. Due to the requirement for quarantine of the ropivacaine prepared by IDS, subject randomization may sometimes deviate from the schedule: a subject scheduled to receive a pump may be placed in the control group if no ropivacaine is available at the time of their surgery, which will be compensated by placing a subsequent subject scheduled to be in the control group into the experimental group when drug is available. These deviations will not be based on subject characteristics, so that assignments remain random, and the total number of control and experimental subjects at each site will remain the same.

Data collection: We will establish an online copy of the SEFAS which subjects can use to enter their responses. This will be done using the REDCap (Research Electronic Data Capture) system for secure web based capture of questionnaire data. For patients opting to have a link to the SEFAS sent to their cell phones, the REDCap-Twillio integration platform will be used. Patients electing not to use the online entry format will be contacted by the research nurse via the preferred route indicated on the consent form, and the research nurse will then enter the data into the Redcap project database. Data from the questionnaires will be exported out of REDCap to be merged with the data from the Medidata Rave® database for analysis. All other data will be entered directly into the Medidata Rave® clinical database. Clinical demographic data will be obtained from the patient at the beginning of the study and verified with the electronic medical record. Analgesic use in the perioperative period will be obtained from the electronic medical chart. Patients typically receive acetaminophen and celecoxib preoperatively, then opioids postoperatively as needed. However, participating in the study will not affect the subjects' options for treatment for pain. Numerical pain ratings recorded in the PACU will be obtained from the electronic medical chart. The Verbal Numerical Scale (VNRS, 0 = no pain, 5 = moderate pain, 10 = worst possible pain) is used for patients in the

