PACU and recorded in the electronic record, until the patient is discharged from the PACU. Chart review of the follow-up orthopedic appointments will be used to identify possible development of chronic pain conditions or unforeseen complications of 5 day pump use.

8. Specimen collection: not applicable.

9. Potential Benefits:

Possible benefits to the subject during the time the pump is in use include better postoperative pain control, improved sleep, and reduced need for opioids with their concomitant side effects and risk of abuse [26]. Preclinical data (see above) and some clinical data in other conditions provide some support for the hypothesis being tested that the nerve block will reduce the risk of chronic pain [27]. If this pilot study is successful and can be extended to a full study large enough to fully test this hypothesis, the research may contribute generalizable knowledge to improve practices in combat medicine and trauma medicine.

10. Potential Risks, Discomforts, and inconveniences:

Level of risk: Greater than minimal risk

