#### **D. Statistical Analysis Plan**

For categorical variables, counts and percentages will be presented. As a check on randomization, groups will be compared using the Fisher's exact test. For continuous variables, mean, median, standard deviation (SD) and inter-quartile range (IQR) will be presented. Groups will be compared using the t-test, except that non-parametric methods will be used for variables distributed non-symmetrically.

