**E. Variables in the analysis data set with Definitions**

Description
Patient unique ID
Age at ankle surgery
Date of ankle surgery
Weight and height at time of surgery
Date of enrollment
Gender
Race
Ethnicity
Randomized to control or experimental group?
Ankle fracture: number of malleoli affected
Grade of injury (defined as :closed injury, or open injury with Gustilo Anderson classification grade 1, grade 2, grade 3a, grade 3b, grade 3cr)
Opioid medication use in PACU: time, agent, dose, and route for each administration
Times entered and discharged from PACU
PACU discharge status (home, rehab facility, hospital, AMA)
Verbal pain scores in PACU (0 – 10 scale) and times at which recorded
Surgical Hardware: number of plates implanted, length and number of screw holes of each.
Estimated blood loss during surgery
Pain medication prescription at discharge (drug, dose)
Start time of surgery
End time of surgery
SEFAS score (2 week, 3, 6, 12 month post surgery)
Subject-reported analgesic use (2 week, 3, 6, 12 month post surgery)
Dates of post-surgical follow-ups (FU)
Weight bearing recommendation at each FU (non, partial, full, other)
Weight bearing current status at each FU [full, assisted (cane, walker, boot), non (crutch)]
Pain status at each FU (none, mild, severe)
Pain medication prescriptions at each FU (drug, dose)
Wound healing status at each FU (dehiscence, cellulitis , deep infection, healing well, other)
Range of motion at each FU
Re-operation required?
Date of re-operation

Indication for re-operation (infection, non-union, hardware failure, hardware removal, other)
Chronic pain conditions diagnosed at one year FU.

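### SAP Table 3 converts wound healing status to an ordinal scale beside a p value, but the five categories are only partly ordered and no code is given (minor)

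*SAP*

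**What the plan says.** Table 3 (Other outcomes) in SAP section I has columns for control, experimental and p value. Two of its rows give wound healing status, at the first and second follow-up visits. The second reads "Wound healing status at second FU (dehiscence, cellulitis , deep infection, healing well, other"), and the first has the same five categories. Both carry footnote 1: "Converted to ordinal scale". The two weight-bearing rows (full, assisted, non) share that footnote.

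The footnote gives no code, range or direction. Section E repeats the list without scores ("Wound healing status at each FU (dehiscence, cellulitis , deep infection, healing well, other"), and section F, which lists the variables to be created, has no wound score. By contrast, the injury-grade footnote in Table 1 reads "Converted to ordinal scale 1 – 6", and PACU discharge status in Table 2 is given a range of 1 to 3.

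Section D gives the general rule: "For categorical variables, counts and percentages will be presented". It names Fisher's exact test as a check on randomization. Section H lists "Calculation of basic statistical parameters, t-tests, Mann-Whitney tests" and Fisher's exact test among the planned calculations. No section names the test for Table 3.

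**The concern.** An ordinal conversion needs an order. Three of the wound categories are different kinds of complication, one is the good outcome and one is a residual class. 'Healing well' is clearly best, and cellulitis can be called milder than deep infection. Dehiscence is a mechanical failure rather than a grade of infection, so it has no fixed place among them. 'Other' could be trivial or serious. The printed order does not help, because it puts 'healing well' fourth, between deep infection and 'other'.

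If the converted values go into a rank test, the p value reflects whichever code is chosen. The trial is open label, so a code not fixed in advance could be chosen with the arms in view. The rows have some safety interest, because Protocol section 7 says that chart review of these visits "will be used to identify possible development of chronic pain conditions or unforeseen complications of 5 day pump use".

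**Working it through.** The plan gives no wound counts, rates or expected p value, so there is no figure to reproduce. The question is whether the plan determines the result.

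**Inputs.** Five categories (SAP section I, Table 3). Forty evaluable subjects (SAP section C), 20 per group (Protocol section 12). All category counts below are assumed. The test is assumed to be a two-sided exact Mann-Whitney test, because the data are made ordinal and section H lists that test.

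**Number of codes.** Five categories can be ordered in 5! = 120 ways. With 'healing well' best, 4! = 24 remain. Requiring cellulitis to be milder than deep infection halves that to 12.

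**Illustration 1.** Pump arm: 14 healing well, 3 cellulitis, 3 other. Control: 20 healing well. That is 6/20 v 0/20 with a problem. The expected rank sum for the pump arm is 20 × 41/2 = 410.
- Printed order: mean ranks are 2 (cellulitis), 20.5 (healing well) and 39 (other). Pump rank sum = 3×2 + 14×20.5 + 3×39 = 410. Deviation 0, p = 1.00.
- 'Healing well' best: its mean rank is 17.5, and the six problems take ranks 35 to 40, which sum to 225. Pump rank sum = 14×17.5 + 225 = 470. Deviation 60, p = 2·C(20,6)/C(40,6) = 2×38,760/3,838,380 = 0.020.
- Fisher's exact test on 6 v 0 gives the same 0.020.
- Of the 120 codes, 80 give 0.020 and 40 give 1.00. The 40 are those that put 'healing well' between cellulitis and 'other'.

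**Illustration 2.** Pump arm: 17 healing well, 3 cellulitis. Control: 17 healing well, 3 other. That is 3/20 v 3/20.
- Printed order: pump rank sum = 3×2 + 17×20.5 = 354.5. Deviation −55.5, p = 2·C(34,17)/C(40,20) = 0.034, although the number of problems is equal.
- 'Healing well' best, then 'other', then cellulitis: 17×17.5 + 3×39 = 414.5. Deviation 4.5, p = 0.70. All 24 codes with 'healing well' best give 0.70; 12 point one way and 12 the other.
- Fisher's exact test on 3 v 3: p = 1.00.

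**Illustration 3, plausible codes only.** Counts in the order dehiscence, cellulitis, deep infection, healing well, other. Control 4/0/1/14/1; pump 0/4/0/11/5.
- Over the 12 codes with 'healing well' best and cellulitis milder than deep infection, p runs from 0.15 to 0.89.
- Fisher's exact test extended to the uncoded 2×5 table gives a single value, about 0.009, because the types of problem differ between arms.

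**The yes/no version also needs a rule.** In illustration 1, if 'other' is not counted as a problem, the comparison becomes 3 v 0 and Fisher's p = 2·C(20,3)/C(40,3) = 2×1,140/9,880 = 0.23 instead of 0.020. In illustration 2 it also becomes 3 v 0, so p moves from 1.00 to 0.23.

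**The case against.** The strongest reply is that the striking figures need a code nobody has proposed. A reader might infer from Tables 1 and 2, whose levels are printed in order and given a range, that wound status will be coded 1 to 5 as printed. The documents do not support that. Footnote 1 gives no range, it covers two variables with different numbers of levels, and a scale that ranks 'healing well' worse than deep infection would not be ordinal in any useful sense. With 'healing well' best, illustration 1 agrees with Fisher's test, and illustration 2 changes only in sign at p = 0.70. This part of the objection stands. What remains is illustration 3: even sensible codes can disagree when the arms differ in the type of complication.

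Second, the test is assumed. If Fisher's exact test is applied to the categories, the code has no effect. That also stands, so the dependence on the code is conditional on a rank test.

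Third, a reader might infer that the conversion would hide an excess of wound problems in the pump arm. Section D already calls for counts and percentages for categorical variables, so the counts should stand beside any p value, and at about 20 per arm a 6 v 0 split would be visible. Pump safety is also watched by other means: daily calls, removal criteria, adverse-event recording, the medical monitor and stopping rules (Protocol sections 6, 10 and 11). None of these uses Table 3.

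**Conclusion.** The flaw is real but minor. Footnote 1 states a rule that does not suit wound healing status, because the list has only a partial order and no code is supplied. If a rank test is used, the p value is not determined by the plan. In the illustrations it moves between 0.020 and 1.00 over all codes, and between 0.15 and 0.89 over the 12 plausible ones. Those sizes rest on assumed counts, 20 patients per arm and an assumed Mann-Whitney test; the gap in the plan does not depend on them.

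Wound status belongs to none of Aims 1 to 4. The SEFAS and PACU results, safety actions and stopping rules are unaffected. Weight-bearing status shares the footnote but is truly ordered, so the conversion is sound there.

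**What to change.** 1. Remove footnote 1 from the two wound rows. Report number (%) in each category by arm, as section D already requires for categorical variables.
2. Name one comparison before analysis. Either use Fisher's exact test on the uncoded categories, which asks whether the mix of categories differs, or use Fisher's exact test on 'healing well' versus not, which asks whether the number of problems differs.
3. For the second choice, fix the handling of 'other' in advance. For example, classify each such case from its chart text without regard to arm, and add a sensitivity count that excludes 'other'.
4. Keep the ordinal scale for weight-bearing status and print the code, for example full = 1, assisted = 2, non = 3.

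The cost is one footnote edit and a few table lines, plus a reading of the chart text for any 'other' cases if the yes/no comparison is chosen. It needs no new data, visits or patients.
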